11.1.1 All Adverse Events

An overview of number of participants (%) with treatment-emergent AEs will be presented for the main AE categories (All AEs, AEs leading to discontinuation, SAEs, SAEs leading to discontinuation, AEs with at least Grade 3 severity (Severe AEs, Life-threatening AEs, Deaths), AEs and SAEs with relationship to IMP as possibly related, probably related, or related) by treatment arm and phase.

11.1.2 Adverse Events Leading to Withdrawal

A data listing of AEs leading to withdrawal will be provided, displaying details of the event(s) captured on the CRF.

11.1.3 Serious Adverse Events

A data listing of SAEs will be provided, displaying details of the event(s) captured on the CRF. Serious adverse event narratives will be provided for the CSR by MediciNova.

11.1.4 Deaths

If any subject dies during the study, relevant information will be supplied in a data listing, and appropriate SAE narratives.

11.2 Pregnancies

Pregnancy data will be shown in a data listing. No special analysis will be performed on the pregnancy data. Participants are to be discontinued from the study if they become pregnant.

11.3 Clinical Laboratory Evaluations

Changes from baseline in laboratory values will be summarized by treatment groups for continuous variables. Lab shift tables showing incidence of new or worsening clinically significant findings from baseline to the last visit will be displayed by treatment groups. Shift from baseline to the highest lab value, and from baseline to the lowest lab value will also be displayed. Incidence of out-of-normal-range values and markedly abnormal change from baseline in laboratory safety test variables will be tabulated by treatment group. Baseline is defined as the last non-missing value prior to the start of study drug infusion.

11.4 Electrocardiogram (ECG)

Descriptive statistics will be presented for ECG measures of PR interval, QRSD interval, QT interval, QTc interval (Fridericia's method), and HR. These statistics will be presented by treatment arm, phase and visit.

The number and percentage of subjects with normal and abnormal ECG results will be summarized by treatment arm, phase, and visit. All ECG measurements will be listed.

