drawn. A serum pregnancy test will be done in non-menopausal females. The use of prior medications taken will be recorded for 7 days prior to Day 1.

Treatment Phase (7 days)

On Day 1 (Baseline) of the Treatment Phase, hospitalized subjects will be treated with MN-166 or placebo for a 7-day period. Subjects will undergo study-related procedures including physical examination, vital signs, clinical status assessment using the NIAID scale, O₂ use and SpO₂, ECG, blood collection of biomarkers, PK (except Day 7), CBC, CMP, D-dimer and coagulation and information on adverse events and concomitant medications will be recorded. (see [Table 1](#) Schedule of Events).

Individual patient stopping criteria based on the known safety profile of ibudilast and study stopping criteria will be implemented (see [protocol sections 12.7](#) and [12.8](#)).

An independent medical safety monitor will evaluate safety on an ongoing basis during the study. After each of the first three subjects are dosed, the medical safety monitor will review the data with the PI and sponsor and will make a recommendation to proceed/stop. After the first three subjects are evaluated, the medical safety monitor will continue to review safety data throughout the study.

Follow-up Phase

The Follow-up Phase consists of three visits, Day 14 (± 3 d), Day 28 (± 3 d) and Day 60 (± 7d).

Day 14

On Day 14, site staff will conduct physical examination, clinical status scale, vital signs and O₂ use, ECG, CBC, CMP, D-dimer, and coagulation tests, biomarkers, AE and conmed review, and record survival status. If subject is no longer hospitalized, a telephone follow-up to record O₂ usage and SpO₂, survival, AEs and conmeds taken will be conducted.

Day 28 (telephone follow-up if patient is no longer hospitalized)

On Day 28, the following assessments will be performed in all subjects: clinical status, O₂ therapy status use, AE and conmed review, and survival status.

Day 60

On Day 60, the following assessments will be performed in all subjects: clinical status, O₂ therapy status, survival status, and AE and conmed review. In addition, vital signs, 12-lead ECG, and clinical safety labs (CBC, CMP, CRP, D-Dimer, PT and INR) will be performed in intubated subjects only.

Discharged prior to Study Day 7

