7.0 SCHEDULE OF ASSESSMENTS

Table 1 Schedule of Assessments

Phase	Screening	Double-Blind Treatment Phase ^{e,g}							Follow-up		
Study Day	Day -3	Day 1 BL	Day 2	Day 3	Day 4	Day 5	Day 6	Day 7	Day 14 ^e (± 3)	Day 28 (+/- 3)	Day 60 (+/- 7d)
Informed consent	X										
Inclusion/exclusion criteria review	X										
Brief physical exam	X	X		X		X		X	X		
Clinical status using NIAID scale	X	X	X	X	X	X	X	X	X	X	X
Vital signs (BP, RR, HR, Temp)	X	X	X	X	X	X	X	X	X		Xⁱ
O₂ therapy status and SpO₂	X	X	X	X	X	X	X	X	X	X	X
12-lead ECG	X	X^a		X^a		X^a		X^a			Xⁱ
Biomarker plasma samples: MIF, IL-1β, IL-6, TNF-α	X^b	X		X		X		X	X		
PK blood sample^c		X		X		X					
CBC, CMP, CRP, D-dimer, PT, INR	X^d	X		X		X		X	X		Xⁱ
Randomize^f	X										
Administer study drug		X^h	X	X	X	X	X	X			
Adverse event review		X	X	X	X	X	X	X	X	X	X

Prior/Concomitant medication review	X	X	X	X	X	X	X	X	X	X	X
Record survival status ^j									X	X	X

^a 12-lead ECG to be done between 2-4 hours after AM dose.

^b Biomarker blood sample collection at screening is optional if Screening and Day 1 assessments occur on the same day.

^c Collect PK samples on Day 1 in the AM prior to study drug dosing and at 2, 4, 8, and 12 hours (Predose of PM dose); Day 3 and Day 5 prior to AM study drug dosing. PK samples to be collected for 8 subjects only.

^d Serum β-hCG for pre-menopausal women.

^e Telephone follow-up if subject is not in hospital. If subject is no longer hospitalized or cannot return due to COVID restrictions, a telephone follow-up to record O₂ usage/levels, AEs and conmeds may be conducted. All other assessments are optional.

^f Subjects may be randomized during the Screening Phase after all of the screening assessments are completed and subject is considered eligible for the study or on Day 1.

^g If subject prematurely discontinues from the study or is discharged from the hospital on Days 2, 4, or 6 collect biomarker samples in addition to other scheduled assessments. If subject prematurely discontinues from the study or is discharged on Days 1, 3, 5, or 7, conduct the study assessments scheduled on those days.

^h The first dose of study drug may be started in the AM or the PM.

ⁱ Vital signs, ECG and safety labs will be done in intubated subjects only.

^j Survival status is captured on the NIAID questionnaire.

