8.8 Previous Human Experience

Ibudilast is approved in Japan and South Korea for treatment of asthma (20 mg/day) and post-stroke dizziness in cerebrovascular disorders (30 mg/day) and has been prescribed for these indications for almost 30 years. The largest accumulation of clinical safety experience with ibudilast (MN-166) is from the approval of Ketas® for asthma and post-stroke dizziness. Dosing was 20 to 30 mg/day (included uses up to 40 mg/day) and based on chronic administration. In the [Ketas package insert](#), the most common adverse events were anorexia (0.6%), nausea (0.6%), increased liver enzymes (ALT 0.4%, AST 0.3%, and GTP 0.4%). Following regulatory approval, adverse event data continued to be collected and, to date, approximately 14,968 subjects were evaluated. Safety data was taken from the 2009 Ketas package insert and Interview Forms collected from 1989 to 1996. Seven hundred sixty-nine (769) adverse drug reactions occurred in 507 (3.39%) patients. The most common ($\geq 5\%$) adverse drug reactions were: itching (8; 0.05%), rash (8; 0.05%), abdominal pain (7; 0.05%), heavy head feeling (7; 0.05%), stomach

pain (7; 0.05%), epigastric discomfort (8; 0.5%), BUN increased (7; 0.05%), heart rate/heart rhythm disorders (8; 0.05%), vertigo (10; 0.7%), serum cholesterol increased (10; 0.07%), general malaise (10; 0.07%), lack of appetite (13; 0.09%), headache (13; 0.09%), heartburn (16; 0.11%), vomiting (19; 0.13%), nausea (22; 0.15%), stomach discomfort (24; 0.16%), ALP increased (36; 0.24%), AST increased (45; 0.30%), ALT increased (53; 0.35%), sickness (54; 0.36%), gamma-GTP increased (54; 0.36%), and anorexia (71; 0.47%).

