Nervous System SOCs. The most commonly reported TEAEs in the ibudilast group were dysphagia, nausea, fatigue, pain, upper respiratory infection, fall, weight loss, anorexia, headache, depression, insomnia, cough, and dyspnea. Treatment-related events that were attributed to ibudilast were decreased/loss of appetite, anorexia/weight loss, nausea, and ECG changes (atrioventricular junctional rhythm), and increased QTcB to upper normal of 470 (Brooks et al 2017).

In the Phase 2 open-label study (MN-166-ALS-1202) a total of 35 subjects with ALS received 100 mg/day up to 9 months. The most commonly reported treatment-related adverse event was nausea.

These studies suggest that ibudilast at daily doses of up to 100 mg/d appear to be generally safe and well-tolerated. The most commonly reported AEs have been nausea, abdominal pain, diarrhea, and headaches. There was a slight dose-related increase in the percent of subjects with headaches and gastrointestinal AEs. The incidence of nausea suggested a dose-related increase. Ibudilast also appeared to cause transient changes in laboratory values, particularly AST, ALT and GGT which, in most cases, appeared to resolve over time.

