11.5 Vital Signs

Changes in vital signs from baseline to each visit will be summarized by treatment groups.

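### SAP 11.4 plans no ECG summary relative to baseline or by QTcF category, and the Day 1 and Day 14 ECG instructions need reconciling

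*Combined protocol and SAP*

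**What the plan says.** **Prior findings.** Among treatment-related events in an ALS study, protocol section 9.1 names "ECG changes (atrioventricular junctional rhythm), and increased QTcB to upper normal of 470". Section 8.8 adds 8 post-marketing reports of heart rate or rhythm disorders among about 14,968 subjects.

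**Collection.** Table 1 has a 12-lead ECG at screening and on Days 1, 3, 5 and 7. At Day 60 there is one for intubated subjects only. The treatment-phase footnote reads "12-lead ECG to be done between 2-4 hours after AM dose". Another footnote to the same table reads "The first dose of study drug may be started in the AM or the PM", and section 13.0 also allows a PM start. For Day 14, the synopsis asks for "ECG, CBC, CMP, D-dimer, and coagulation tests, biomarkers, AE and conmed review, and record survival status". Table 1, sections 11.3 and 15.3.3, and both schedules in SAP 13 show no Day 14 ECG.

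**Analysis.** SAP 11.4 begins "Descriptive statistics will be presented for ECG measures of PR interval, QRSD interval, QT interval" and continues with QTcF and heart rate. It then says "These statistics will be presented by treatment arm, phase and visit", and adds counts of normal and abnormal ECGs on the same breakdown. SAP 7 defines descriptive statistics to include the minimum and maximum at each time-point. For vital signs, SAP 11.5 says "Changes in vital signs from baseline to each visit will be summarized by treatment groups". For laboratory values, SAP 11.3 plans change from baseline, shifts to the last, highest and lowest value, and counts of markedly abnormal change.

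**Baseline.** SAP 7.2 takes the closest measurement before the first dose. SAP 7.3 labels Day 1 as baseline.

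**The concern.** QTc prolongation is a matter of individual subjects, and the informative quantity is each subject's change from a pre-dose ECG. The trial collects what is needed: a pre-dose screening ECG and up to four treatment-phase ECGs. SAP 11.4 never subtracts one from the other, takes no worst on-treatment value and counts no one by size of QTcF or of change. Laboratory values receive all of these in some form.

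The Day 1 and Day 14 instructions bear on the same question. If a Day 1 ECG recorded after the first dose is read as baseline because of the visit label, an early drug effect is subtracted out of any later comparison. If there is no Day 14 ECG, a non-intubated subject who completes dosing has no scheduled ECG off drug, so reversal of a change seen on treatment cannot be checked.

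**Working it through.** The plan gives no figure for ECG to reproduce. The check sets the passages side by side and then sizes the gap.

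**1. Planned analyses by safety domain**

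| | Values by visit | Change from baseline | Shift | Extreme or category counts |
|---|---|---|---|---|
| Laboratory (SAP 11.3) | yes | yes | yes | yes |
| Vital signs (SAP 11.5) | not restated | yes | no | no |
| ECG (SAP 11.4) | yes, with maximum | no | no | normal/abnormal only |

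ECG is also missing from the list of safety categories that opens SAP 11, and it has no table in SAP 13.3. SAP 13.4 has two ECG listings.

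**2. What the planned summaries can miss**

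Inputs: 31 subjects consented under Amendment 2 and 5 under Amendment 4 (SAP 13.1 and 13.2), so 36 in all and about 36/2 = 18 per arm. The number randomised is not given, so the planned 20 per arm (40/2) is shown as well. The 60 ms rise and the between-subject QTc SD of 20 to 30 ms are assumptions for illustration.

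- Shift in the arm mean from one subject: 60/18 = 3.3 ms, or 60/20 = 3.0 ms.
- Standard error of the mean, SD/√n: 20/√18 = 4.7 and 30/√18 = 7.1 ms. With n = 20 these are 4.5 and 6.7 ms.
- The shift is below one standard error in every case, so the mean does not show it.
- The maximum moves only if the subject becomes the highest in the arm at that visit. If another subject already stands at, say, 470 ms, anyone starting at 470 − 60 = 410 ms or lower can rise by 60 ms without changing it.
- If the resulting ECG is read as normal, the normal/abnormal count does not move either.

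**3. Is precision the reason for change from baseline?**

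For a within-subject correlation r, SD of change / SD of value = √(2(1 − r)). The documents give no r:

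| r | 0.3 | 0.5 | 0.7 | 0.8 |
|---|---|---|---|---|
| ratio | 1.18 | 1.00 | 0.77 | 0.63 |

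The arm mean of change is more precise only if r exceeds 0.5. The argument therefore rests on seeing individual change, not on tighter means.

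**4. Day 1**

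For an AM starter, an ECG 2 to 4 hours after the AM dose follows the first dose, although the visit is labelled baseline. SAP 7.2 then points to the screening ECG. A PM starter has no AM dose on Day 1, so the ECG time is undefined. On the schedules supplied, the AM/PM footnote appears only under Amendment 4: 5/36 = 13.9% of those consented. The full Amendment 2 text is not available, so PM starts among the other 31 cannot be excluded.

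**5. Last ECG against last dose**

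The Day 7 ECG follows the AM dose. The final dose comes later, in the evening of Day 7 or, for PM starters, on the morning of Day 8 (section 13.0). Outside the synopsis, the only later ECG is at Day 60, for intubated subjects.

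**The case against.** The strongest reply is that the plan shows more than means. The maximum QTcF is tabulated for each arm and visit, abnormal ECGs are counted, every ECG is listed, and an ECG finding judged to be an adverse event enters the TEAE tables. A reader might infer that marked prolongation would be visible only in a listing. The documents do not support that, since a high absolute value reaches the summary tables. What stands is narrower: the within-subject change is not summarised.

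Four other inferences also go too far.

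- **QTc as an established ibudilast risk.** The protocol describes the QTcB value as upper normal, the post-marketing reports are 8 of 14,968 (0.05%), and no ECG item is among the stopping criteria in section 12.7. These are reported treatment-related events, and no more.
- **A Day 1 row known to mix pre-dose and post-dose ECGs.** A PM starter's Day 1 ECG could be before the dose, after it or not done. The text does not say.
- **No off-drug ECG for any non-intubated subject.** Subjects who stop drug early stay on scheduled assessments (sections 12.6, 12.7 and 13.5) and may have one. The gap concerns those who complete dosing.
- **The missing table as a sign of ECG neglect.** Vital signs have no table in SAP 13.3 either.

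It is also fair to say that SAP 7.2 already gives a pre-dose baseline. That rule is sound, but SAP 11.4 makes no use of it, and the Day 1 label in SAP 7.3 invites a different reading.

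**Conclusion.** The point holds in limited form. SAP 11.4 analyses nothing relative to baseline or to a QTcF category, so a large rise ending at an unremarkable absolute value could appear in no ECG summary. The sizes above depend on assumed values (60 ms, SD 20 to 30 ms, 18 to 20 per arm). The absence of a change analysis is plain from the text and needs no assumption.

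The Day 14 conflict between the synopsis and the other sections is a direct contradiction. The Day 1 timing rule does not cover a permitted PM start. How many subjects that affects is unknown; the supplied schedules tie it to 5 of 36 consented.

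This is descriptive safety reporting in a proof-of-concept trial of about 40 subjects. ECG is not among the listed endpoints, and no primary or secondary efficacy conclusion depends on it. It is worth correcting because the ECGs are already scheduled and the analysis is simple.

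**What to change.** **SAP 11.4**

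- Add change in QTcF, PR and heart rate from the last pre-dose ECG (the SAP 7.2 rule) by arm and visit.
- Add each subject's worst post-dose QTcF, with counts by arm in prespecified value and change categories. The documents state no cut-offs. The SAP names ICH E14 among the documents reviewed, so the sponsor should choose the categories and write them in.
- Add a normal-to-abnormal shift from the last pre-dose ECG.
- State that a Day 1 ECG recorded after the first dose is a post-dose value, whatever the visit label, and classify Day 1 ECGs by recorded dose time.

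**SAP 11 and 13.3**

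- Name ECG among the safety categories and add the matching table.

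**Protocol**

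- Reconcile the Day 14 ECG between the synopsis and Table 1, sections 11.3 and 15.3.3 and the SAP schedules. The synopsis replaces the Day 14 visit by telephone contact once a subject has left hospital, so the reconciled text should also say to whom any ECG applies.
- Reconcile the Day 1 ECG timing footnote with the permitted PM first dose.

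**Cost.** One or two descriptive tables from ECGs already scheduled, plus wording changes. Cell counts will be small and should be reported without testing.

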11.5 Vital Signs

Changes in vital signs from baseline to each visit will be summarized by treatment groups.

11.6 Physical examination

Physical examination results will be included in data listings only.

13 APPENDICES

13.1 Schedule of Assessments (Amendment 2)

Phase	Screening	Double-Blind Treatment Phase ^{d,f}							Follow-up	
		Day -3	Day 1 BL	Day 2	Day 3	Day 4	Day 5	Day 6	Day 7	Day 14 ^d (± 3)
Study Day										
Informed consent	X									
Inclusion/exclusion criteria review	X									
Brief physical exam	X	X		X		X		X	X	
Clinical status using NIAID scale	X	X	X	X	X	X	X	X	X	X
Vital signs (BP, RR, HR, Temp)	X	X	X	X	X	X	X	X	X	
O₂ therapy status and SpO₂	X	X	X	X	X	X	X	X	X	
12-lead ECG	X	X^a		X^a		X^a		X^a		
Biomarker plasma samples: MIF, IL-1β, IL-6, TNF-α	X	X		X		X		X	X	
PK blood sample^b		X		X		X				
CBC, CMP, CRP, D-dimer, PT, INR	X^c	X		X		X		X	X	
Randomize^e	X									
Administer study drug		X	X	X	X	X	X	X	X	
Adverse event review		X	X	X	X	X	X	X	X	
Prior/Concomitant medication review	X	X	X	X	X	X	X	X	X	
Record survival status										X

^a 12-lead ECG to be done between 2-4 hours after AM dose.

^b Collect PK samples on Day 1 in the AM prior to study drug dosing and at 2, 4, 8, and 12 hours (Predose of PM dose); Day 3 and Day 5 prior to AM study drug dosing. PK samples to be collected for 8 subjects only.

^c Serum β-hCG for pre-menopausal women.

^d Telephone follow-up if subject is not in hospital. If subject is no longer hospitalized or cannot return due to COVID restrictions, a telephone follow-up to record O₂ usage/levels, AEs and conmeds may be conducted. All other assessments are optional.

^e Subjects may be randomized during the Screening Phase after all of the screening assessments are completed and subject is considered eligible for the study or on Day 1.

^f If subject prematurely discontinues from the study or is discharged from the hospital on Days 2, 4, or 6 collect biomarker samples in addition to other scheduled assessments. If subject prematurely discontinues from the study or is discharged on Days 1, 3, 5, or 7, conduct the study assessments scheduled on those days.

^gThirty-one (31) subjects were consented under Protocol amendment 2.

13.2 Schedule of Assessments (Amendment 4)

Phase	Screening	Double-Blind Treatment Phase ^{e,g}							Follow-up		
		Day 1 BL	Day 2	Day 3	Day 4	Day 5	Day 6	Day 7	Day 14 ^c (± 3)	Day 28 (±3)	Day 60 (±7)
Study Day	Day -3										
Informed consent	X										
Inclusion/exclusion criteria review	X										
Brief physical exam	X	X		X		X		X	X		
Clinical status using NIAID scale	X	X	X	X	X	X	X	X	X	X	X
Vital signs (BP, RR, HR, Temp)	X	X	X	X	X	X	X	X	X		X ⁱ
O₂ therapy status and SpO₂	X	X	X	X	X	X	X	X	X	X	X
12-lead ECG	X	X ^a		X ^a		X ^a		X ^a			X ⁱ
Biomarker plasma samples: MIF, IL-1β, IL-6, TNF-α	X ^b	X		X		X		X	X		
PK blood sample^c		X		X		X					
CBC, CMP, CRP, D-dimer, PT, INR	X ^d	X		X		X		X	X		X ⁱ
Randomize^f	X										
Administer study drug		X ^h	X	X	X	X	X	X			
Adverse event review		X	X	X	X	X	X	X	X	X	X
Prior/Concomitant medication review	X	X	X	X	X	X	X	X	X	X	X
Record survival status^j									X	X	X

^a 12-lead ECG to be done between 2-4 hours after AM dose.

^b Biomarker blood sample collection at screening is optional if Screening and Day 1 assessments occur on the same day.

^c Collect PK samples on Day 1 in the AM prior to study drug dosing and at 2, 4, 8, and 12 hours (Predose of PM dose); Day 3 and Day 5 prior to AM study drug dosing. PK samples to be collected for 8 subjects only.

^d Serum β-hCG for pre-menopausal women.

^e Telephone follow-up if subject is not in hospital. If subject is no longer hospitalized or cannot return due to COVID restrictions, a telephone follow-up to record O₂ usage/levels, AEs and conmeds may be conducted. All other assessments are optional.

^f Subjects may be randomized during the Screening Phase after all of the screening assessments are completed and subject is considered eligible for the study or on Day 1.

^g If subject prematurely discontinues from the study or is discharged from the hospital on Days 2, 4, or 6 collect biomarkers samples in addition to other scheduled assessments. If subject prematurely discontinues from the study or is discharged on Days 1, 3, 5, or 7, conduct the study assessments scheduled on those days.

^h The first dose of study drug may be started in the AM or the PM.

ⁱ Vital signs, ECG and safety labs will be done in intubated subjects only.

Survival status is captured on the NIAID questionnaire.

^j Five (5) subjects were consented under Amendment 4.

13.3 List of Tables

Table Number	Table Description
14.1	Demographic Data
14.1.1	Subject Disposition (including discontinued subjects)
14.1.2	Summary of Protocol Deviations
14.1.3	Demographics and Baseline Characteristics
	Summary of Disease Characteristics at Baseline by Treatment
14.1.4	Summary of Medical History
14.1.5	Prior and Concomitant Medications (Safety Population)
14.1.6	Study Drug Exposure
14.2	Efficacy
14.2.1	Number (%) of subjects free from respiratory failure at Day 7
14.2.2	Number (%) of subjects with at least a 1-point improvement in clinical status using the NIAID 8-point ordinal scale at Day 7
14.2.3	Number (%) of subjects free from respiratory failure at Days 14, 28, and 60
14.2.4	Number (%) of subjects with mechanical ventilation/intubation at Days 7, 14, 28, and 60
14.2.5	Change from baseline in clinical status using the NIAID 8-point ordinal scale at Days 7, 14, 28, and 60
14.2.6	Number (%) of subjects with at least a 1-point improvement in clinical status using the NIAID 8-point ordinal scale at Days 14, 28, and 60
14.2.7	Number (%) of subjects discharged from hospital at Days 7, 14, 28, and 60
14.2.8	All-cause mortality at Days 28 and 60
14.3	Safety
14.3.1	Summary of Treatment-emergent adverse events by Treatment
14.3.1.1	Incidence of TEAEs MedDRA System Organ Class and Preferred Term by Treatment
14.3.1.2	Incidence of TEAEs Occurring in more than 5% of Subjects by Treatment
14.3.1.3	Incidence of Post-treatment AEs by Treatment
14.3.1.4	Incidence of TEAEs by MedDRA System Organ Class, Preferred Term and Severity
14.3.1.5	Incidence of Treatment-Emergent Adverse Events by MedDRA System Organ Class, Preferred Term and Relationship to Study Drug
14.3.1.6	Incidence of Treatment-Emergent Adverse Events by MedDRA System Organ Class, Preferred Term, Relationship to Study Drug, and Severity
14.3.2	Incidence of Serious Treatment-Emergent Adverse Events by MedDRA System Organ Class and Preferred Term
14.3.3	Incidence of Serious Treatment-Emergent Adverse Events by MedDRA System Organ Class, Preferred Term and Severity
14.3.4	Incidence of Serious Treatment-Emergent Adverse Events by MedDRA System Organ Class, Preferred Term and Severity
14.3.4.1	Incidence of Subjects with Serious Treatment-Emergent Adverse Events by MedDRA System Organ Class, Preferred Term and Relationship
14.3.4.2	Incidence of Serious Treatment-Emergent Adverse Events by MedDRA System Organ Class, Preferred Term and Relationship
14.3.4.3	Incidence of Serious Treatment-Emergent Adverse Events by MedDRA System Organ Class, Preferred Term, Relationship and Severity
14.3.4.4	Incidence of TEAEs Leading to Early Termination by Treatment

Confidential

14.3.4.5	Incidence of Deaths by Treatment
14.3.4.6	Incidence of TEAEs by Maximum Severity by Treatment
14.3.4.7	Summary of Clinical Laboratory Data: Clinical Chemistry by Treatment
14.3.4.8	Summary of Clinical Laboratory Data: Clinical Hematology by Treatment
14.3.4.9	Shifts from Baseline of Clinical Laboratory Data: Clinical Chemistry – Shift from Baseline to the Last Visit
14.3.4.10	Shifts from Baseline of Clinical Laboratory Data: Clinical Hematology by Treatment

Confidential

